17.2.2 Microbiological Assessments

17.2.2.1 Respiratory Culture and Gram Stain

At the Screening visit collection of an adequate quality expectorated or induced sputum or other respiratory specimen reflecting fluid from the lower respiratory tract (eg, respiratory fluid obtained by bronchoalveolar lavage or bronchoscopy; pleural fluid obtained by thoracentesis; or expectorated or induced sputum meeting adequacy criteria) should be attempted from all subjects and submitted to the local microbiology laboratory for Gram stain and culture (see [STUDY FLOWCHART](#)). The date, time and type of specimen submitted will be recorded on source documents at the local laboratory. These specimens may be obtained as part of routine, non-study evaluation of a subject being evaluated for CABP and therefore could be obtained prior to obtaining informed consent.

An adequate quality sputum specimen will be defined as having the following 2 findings as reported by the local laboratory:

1. < 10 Squamous epithelial cells/low power field (lpf) (ie, 100 \times)
2. > 25 Polymorphonuclear cells/lpf (ie, 100 \times)

Adequate quality sputum specimens and other Screening respiratory specimens for culture should be obtained prior to first dose of test article. In the event that a sputum specimen is determined to be inadequate, or cannot be obtained prior to the first dose of test article, collection of a specimen should be attempted within 24 hours after the first dose of test article. As the infection responds to therapy, obtaining repeated specimens for culture or examination may not be clinically appropriate and/or there may be no material for culture. At the EOT and/or PTE visit, respiratory specimen cultures and Gram stains should be obtained only for subjects who are Clinical Failures and require alternative antibacterial treatment for CABP.

All respiratory and blood specimens submitted to the local laboratory are to be processed for a Gram stain of the specimen and for aerobic culture. Laboratory reports on Gram stains should include a semi-quantitative description of the number of polymorphonuclear leukocytes per low power field (ie, 100 \times) and a description of bacteria seen. For Gram stains of respiratory

specimens a semi-quantitative description of the number of squamous epithelial cells per low power field (ie, 100 \times) should also be included.

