5.2.2.2 Microbiologic Outcomes

Microbiological response definitions for the evaluations performed at the EOT and PTE Visits and analyzed in the microITT and ME populations are presented in the table below. Post-baseline microbiological samples will be collected only as clinically indicated. Atypical pathogens identified only by acute and convalescent serology or baseline urinary antigen tests (UAT), and *Streptococcus pneumoniae* identified only by baseline UAT can only have a presumed or indeterminate microbiologic response.

If a subject has the same pathogen (ie, same genus and species) identified from both a respiratory and blood specimen, a microbiological response is determined for each of the pathogens. The microbiologic response for the respiratory pathogen is based on the pathogen isolated from the EOT or PTE specimen, if a specimen was collected. The microbiologic response for the blood pathogen is based on the blood sample collected at EOT or PTE, or if a sample was not collected at the post-baseline visit, the blood sample collected prior to and closest to the visit. For the pathogen specific microbiologic response, the worst outcome for the pathogen should be summarized. If *Streptococcus pneumoniae* is identified from both a UAT and a culture, the culture should be used to determine microbiological response.

Table 4. Per-Pathogen Microbiological Response Definitions at the EOT and PTE Visits

Term	Definition
Eradication	The baseline pathogen based on culture was absent from repeat culture(s) of the same sample type (blood or respiratory specimen).
Presumed Eradication	No post-baseline source specimen to culture in a subject assessed with a clinical success by the Investigator
Persistence	The baseline pathogen based on culture was present in repeat culture(s) of the same sample type (blood or respiratory specimen).
Presumed Persistence	No post-baseline source specimen to culture in a subject assessed with a clinical failure by the Investigator
Indeterminate	The subject's clinical response is indeterminate or other circumstance that precludes a microbiological evaluation

Abbreviations: EOT = end of treatment; PTE = post-therapy evaluation.

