Microbiological outcomes are further categorized as favorable, unfavorable, and indeterminate. Favorable microbiological outcomes are defined as eradication or presumed eradication. Unfavorable microbiological outcomes are defined as persistence or presumed persistence. Microbiological response will be derived using electronic microbiology data from the central laboratory and from pathogen determination provided by the Sponsor for each baseline isolate.

Overall microbiological response at PTE is determined as follows from the microbiological responses at the EOT and PTE Visits:

Table 5. Per-Pathogen Microbiologic Response

EOT Visit	PTE Visit	Overall Microbiologic Response at PTE
Favorable	Favorable	Favorable
Favorable	Unfavorable	Unfavorable
Favorable	Indeterminate	Indeterminate
Unfavorable	Favorable	Unfavorable
Unfavorable	Unfavorable	Unfavorable
Unfavorable	Indeterminate	Unfavorable
Indeterminate	Favorable	Indeterminate
Indeterminate	Unfavorable	Unfavorable
Indeterminate	Indeterminate	Indeterminate

Abbreviations: EOT = end of treatment; PTE = post-therapy evaluation.

Note: Favorable is defined as eradication or presumed eradication. Unfavorable is defined as persistence or presumed persistence.

Per-subject responses will be based on per-pathogen responses. To have an overall per-subject favorable microbiologic response, the outcome for each baseline pathogen must be favorable (eradicated or presumed eradicated). If the outcome for any pathogen is unfavorable (persistence or presumed persistence), the subject will be considered to have an unfavorable per-subject microbiologic response. Subjects with an indeterminate response for all pathogens will be considered to have an indeterminate per-subject microbiologic response. If the same pathogen is isolated from multiple sample types (blood, respiratory, urine), the worst outcome will be used to determine per-subject microbiologic response. Superinfections will not be considered in the microbiological response. Microbiological response from worst to best are as follows: persistence, presumed persistence, indeterminate, presumed eradication, and eradication.

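### SAP 5.2.2.2 gives two unreconciled rules for S. pneumoniae found by both urinary antigen and culture, so the descriptive per-subject response can contradict the per-pathogen response

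*Combined protocol and SAP*

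**What the plan says.** All of the derivation rules are in SAP 5.2.2.2.

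- **Culture rule.** When *S. pneumoniae* "is identified from both a UAT and a culture, the culture should be used to determine microbiological response". The sentence is not confined to the per-pathogen or the per-subject level.
- **Worst-outcome rule.** "If the same pathogen is isolated from multiple sample types (blood, respiratory, urine), the worst outcome will be used to determine per-subject microbiologic response". It names urine and makes no exception for *S. pneumoniae*.
- **Link between levels.** "Per-subject responses will be based on per-pathogen responses".
- **UAT-only findings.** *S. pneumoniae* "identified only by baseline UAT can only have a presumed or indeterminate microbiologic response".
- **Table 4.** Eradication is defined as "The baseline pathogen based on culture was absent from repeat culture(s) of the same sample type (blood or respiratory specimen". Presumed Persistence is "No post-baseline source specimen to culture in a subject assessed with a clinical failure by the Investigator".
- **Ranking.** "Microbiological response from worst to best are as follows: persistence, presumed persistence, indeterminate, presumed eradication, and eradication".

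On specimens, protocol 17.2.2.1 says that at EOT and PTE "respiratory specimen cultures and Gram stains should be obtained only for subjects who are Clinical Failures and require alternative antibacterial treatment for CABP". Protocol 17.2.2.2 limits urine pathogen testing to the *Legionella pneumophila* and *S. pneumoniae* antigens.

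**The concern.** Because the antigen tests are the only urine tests for pathogens, urine in the worst-outcome sentence can only mean the UAT. That sentence therefore reaches the case the culture rule has already decided, and it can decide it the other way. A subject with *S. pneumoniae* as the only baseline pathogen could be counted as favorable in the per-pathogen table and unfavorable in the per-subject table, although the SAP says the second is built from the first.

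Three outputs in SAP 10.4 are at stake: the per-subject favorable rate (microITT and ME populations), its 95% CI, and the microITT concordance of clinical and microbiological response at PTE. For concordance, the choice of rule decides whether such a clinical failure appears as agreement or disagreement.

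**Working it through.** The plan gives no figure for this derivation, so the check applies the two rules to every possible case. Take a subject whose only baseline pathogen is *S. pneumoniae*, found by UAT and by culture from one source.

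**Inputs.** Clinical response is success, failure or indeterminate. Repeat culture is none, negative or positive. Under Table 4 a negative repeat is Eradication (E) and a positive repeat is Persistence (P). With no repeat, the outcome follows clinical response: Presumed Eradication (PE), Presumed Persistence (PP) or Indeterminate (I). The UAT component has nothing to culture, so it always follows clinical response. E and PE are favorable; P and PP are unfavorable.

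| Clinical response | Repeat culture | Culture rule | Worst of culture and UAT |
|---|---|---|---|
| Success | none | PE, favorable | PE, favorable |
| Success | negative | E, favorable | PE, favorable |
| Success | positive | P, unfavorable | P, unfavorable |
| Failure | none | PP, unfavorable | PP, unfavorable |
| **Failure** | **negative** | **E, favorable** | **PP, unfavorable** |
| Failure | positive | P, unfavorable | P, unfavorable |
| Indeterminate | none | I | I |
| **Indeterminate** | **negative** | **E, favorable** | **I** |
| Indeterminate | positive | P, unfavorable | P, unfavorable |

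The rules disagree in 2 of 9 cells.

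**Combining EOT and PTE with SAP Table 5.** There are 9 × 9 = 81 combinations. Under the culture rule, 4 cells are favorable, so 4 × 4 = 16 combinations are favorable overall. Under the worst-outcome rule, 2 cells are favorable, giving 2 × 2 = 4.

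- Of the 16 − 4 = 12 that change, 16 − 9 = 7 include the failure-with-negative-culture cell and become unfavorable. The other 5 become indeterminate.
- Two more move from indeterminate to unfavorable.
- In total, 12 + 2 = 14 of 81 differ, and 7 of those go from favorable to unfavorable.

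These counts show where the rules conflict. They are not frequencies, and many of the combinations will be rare. With one rule at both levels, all 9 cells and all 81 combinations agree.

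**More than one cultured source.** SAP 5.2.2.2 already takes the worst outcome across blood and respiratory cultures for a pathogen. If one culture-positive source has no repeat in a clinical failure, that source is Presumed Persistence and both rules give unfavorable. Divergence therefore needs negative repeats for every culture-positive source.

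**Size.** The plan's microITT figure is 27% of 750: 0.27 × 750 = 202.5, stated as 202. Per arm that is 202 / 2 = 101. One reclassified subject moves the arm's per-subject rate by 1 / 101 = 0.0099, or about 1.0 percentage point.

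**The case against.** The best counter-reading is that the culture rule is the specific one and comes first. The UAT has been set aside before the per-subject step, and the worst-outcome sentence chooses only among what remains. In support, the SAP gives the UAT a presumed outcome only when it is the sole source of identification. Treating the UAT as a separate urine source with its own Presumed Persistence is an inference from Table 4; the SAP does not state it. This reading is reasonable and may be what was intended. But no sentence gives the culture rule precedence, SAP 6.1.3, 8.3, 9.2.1 and 10.4 are silent, and the worst-outcome sentence names urine. A programmer following it literally would produce the split result.

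The indeterminate cell is only arguable, because Table 4 also defines Indeterminate by an indeterminate clinical response. On that reading both rules give Indeterminate there, and only the clinical-failure cell diverges.

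It is also fair to object that the pattern is narrow and the analyses are supportive. Both points stand. The narrow group is nonetheless one the protocol can generate: repeat respiratory cultures at EOT and PTE are reserved for clinical failures needing alternative treatment, and positive blood cultures are repeated until negative (protocol 16.1.4.3). SAP Appendix 1 still shows a urine antigen test at PTE, which protocol 17.2.2.2 does not, but Table 4 defines Eradication and Persistence by culture, so the result is the same.

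**Conclusion.** The conflict is real and confined to the per-subject microbiological response. Its size is about 1 percentage point per affected subject in a microITT arm of about 101. The documents do not say how many subjects would be affected; the number may be zero. The divergence assumes that the UAT is read as a separate source and that every culture-positive source has a negative repeat.

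A reader might infer more than the documents support:

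- **That the per-pathogen *S. pneumoniae* row also shifts.** It does not: the worst-outcome sentence naming urine governs only the per-subject response, and the culture rule settles that row.
- **That every bacteremic, UAT-positive failure whose blood clears is affected.** A positive baseline sputum with no repeat makes both rules agree.
- **That a shift can be stated for the ME populations.** The 80% in the sample-size section is the CE evaluability rate; no ME size is given.
- **That *L. pneumophila* is a second contradiction.** The SAP has no culture rule for it, so treating it differently is a design choice.

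The intervals are descriptive and no non-inferiority conclusion is drawn from them (SAP 10.4). Early Clinical Response, PTE clinical response and the non-inferiority test are untouched.

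**What to change.** In SAP 5.2.2.2, add to the worst-outcome sentence: *except that when S. pneumoniae is identified by both UAT and culture, only the culture outcome(s) are used, as for the per-pathogen response.* Program this one rule at both levels and settle it before unblinding, so that the handling of these subjects is not chosen after results are seen.

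The cost is one clause and one line of derivation code, with no new data. Extending culture precedence to *L. pneumophila* is optional, and no serology rule is needed to resolve the conflict.

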5.3 Safety Measures

The safety parameters include AEs, clinical laboratory evaluations, vital signs, and ECG findings. AEs will be coded using the Medical Dictionary of Regulatory Activities (MedDRA) Version 17.1 or higher to the System Organ Class and Preferred Term levels.

5.4 Pharmacokinetic Parameters

The concentration of omadacycline will be obtained from plasma samples. Refer to the pharmacokinetic analysis plan for further details.

6 STUDY POPULATIONS

6.1 Analysis Populations

6.1.1 Intent-to-Treat (ITT) Population

The ITT population will consist of all randomized subjects regardless of whether or not the subject received test article. A subject is considered randomized when the IxRS provides the test article assignment (ie, completes a randomization transaction).

6.1.2 Safety Population

The Safety population will consist of all randomized subjects who receive test article (either active or placebo). All safety analyses will be conducted in this population.

6.1.3 Microbiological Intent-to-Treat (microITT) Population

The microITT population will consist of all subjects in the ITT population who have at least one causative bacterial pathogen identified from a culture of a respiratory specimen (eg, respiratory fluid obtained by bronchoalveolar lavage [BAL] or bronchoscopy; pleural fluid obtained by thoracentesis; or expectorated or induced sputum meeting adequacy criteria as defined by the Gram stain results), culture of blood or from a culture-independent method (eg, positive urinary antigen test for *Streptococcus pneumoniae* or *Legionella pneumophila*, or positive serology for *Legionella pneumophila*, *Mycoplasma pneumoniae*, or *Chlamydophila pneumoniae*) at baseline.

Pathogen determination of typical bacteria is based on the genus and species identification from the central laboratory. If the local laboratory grows an acceptable pathogen but the central laboratory is not able to grow the isolate, if isolates are lost during transportation or storage, or there are major discrepancies between the local and central laboratory in the identification of species, the central laboratory or other Sponsor designee will request that the local laboratory resend the isolate. If the central laboratory cannot determine the genus and species of the isolate for any reason, the local laboratory determination of genus and species will be used for pathogen identification. The central laboratory identification of genus and species is used for analysis unless no central determination exists in which case the local laboratory determination is used.

In general, baseline is defined as the 24-hour period prior to the administration of the first dose of test article. However, if the subject is unable to produce a sputum sample at baseline or the sputum sample is not adequate based on the Gram stain criteria, a specimen obtained within 24 hours after the first dose of test article may be considered a baseline sample. If the sputum sample collected in the 24-hour period prior to the administration of the first dose of test article is not adequate based on the Gram stain criteria and the sputum sample obtained within 24 hours after the first dose of test article is not adequate based on the Gram stain criteria, only the sputum sample collected in the 24-hour period prior to administration of the first dose of test article will be considered baseline. UAT samples up through 24 hours after the first dose of test article may be considered the baseline sample, if a previous sample was

not taken or was found to be negative. Blood samples up through 24 hours after the first dose of test article may be considered the baseline sample, if a previous sample was not taken or was found not to have a pathogen.

The following isolates will always be considered a pathogen:

Streptococcus pneumoniae

- Positive BAL, bronchoscopy, pleural fluid, or blood culture; or
- Positive sputum culture in the presence of an adequate Gram stain defined as having > 25 polymorphonuclear neutrophils (PMNs)/Low Power Field (LPF) and < 10 Squamous Epithelial Cells (SECs)/LPF; or
- Positive urinary antigen test

Haemophilus influenzae

- Positive BAL, bronchoscopy, pleural fluid, or blood culture; or
- Positive sputum culture in the presence of an adequate Gram stain (> 25 PMNs/LPF and < 10 SECs/LPF)

Staphylococcus aureus

- Positive BAL, bronchoscopy, pleural fluid, or blood culture
- Positive sputum culture in the presence of an adequate Gram stain (> 25 PMNs/LPF and < 10 SECs/LPF)

Moraxella catarrhalis

- Positive BAL, bronchoscopy, pleural fluid, or blood culture; or
- Positive sputum culture in the presence of an adequate Gram stain (>25 PMNs/LPF and < 10 SECs/LPF)

Legionella pneumophila

- Positive BAL, bronchoscopy, pleural fluid, or blood culture; or
- Positive sputum culture, regardless of Gram stain findings; or
- Positive acute (baseline) or positive convalescent (PTE) IgM (Euroimmun IgM ELISA OD ratio of ≥ 1.1)
- Negative acute (baseline) and positive or indeterminate convalescent (PTE) IgG (Euroimmun IgG ELISA OD ratio of ≥ 1.1)
- A positive urine antigen test

Mycoplasma pneumoniae

- Positive acute (Baseline) or positive convalescent (PTE) IgM (Euroimmun IgM ELISA OD ratio of ≥ 1.1)
- Negative acute (Baseline) and positive or indeterminate convalescent (PTE) IgG (Euroimmun IgG ELISA OD ratio of ≥ 1.1)

Chlamydophila pneumoniae

- Positive acute (Baseline) or positive convalescent (PTE) IgM (SeroCP™ IgM cut-off index of > 1.5)
- Negative acute (Baseline) and positive or indeterminate convalescent (PTE) IgG (SeroCP™ IgG cut-off index of > 1.1)

The following isolates are considered as contaminants from respiratory specimens rather than pathogens of CABP: fungi, *Enterococcus* spp., viridans streptococci, coagulase-negative staphylococci, *Micrococcus* spp., *Neisseria* spp. other than *N. meningitidis*, *Corynebacterium* spp. and other coryneforms, *Lactobacillus* spp., *Vibrio* spp., *Capnocytophaga* spp., *Cardiobacterium* spp., *Flavobacterium* spp.

Other isolates identified from culture of blood and respiratory specimens will be reviewed in a blinded manner by the Sponsor on a case-by-case basis for determination of whether the organism is a pathogen for CABP.

An expanded microITT population will also be analyzed. The expanded microITT population will be defined using the same criteria as for the microITT population except an adequate Gram stain will be defined as > 10 PMNs/LPF and < 10 SECs/LPF for determination of whether an isolate from a sputum culture is a pathogen or not.

Staphylococcus aureus will be considered a distinct pathogen with methicillin-resistant *Staphylococcus aureus* (MRSA) and methicillin-susceptible *Staphylococcus aureus* (MSSA) considered distinct pathogens. Likewise, *Streptococcus pneumoniae* will be a distinct pathogen with penicillin-nonsusceptible *Streptococcus pneumoniae* (PNSSP), penicillin-susceptible *Streptococcus pneumoniae* (PSSP), macrolide-resistant *Streptococcus pneumoniae*, quinolone-resistant *Streptococcus pneumoniae*, and multiple drug resistant *Streptococcus pneumoniae* (MDRSP) each considered distinct pathogens. A pathogen will be considered multiple drug resistant if susceptibility testing shows resistance to 3 or more of the classes of antibiotics provided below except in the case of MRSA where penicillin and cephalosporin are due to a single mechanism in which case 2 non- β -lactam resistances in addition to oxacillin, will be considered multi-drug resistant. *Streptococcus* spp. and *Staphylococcus* spp., isolates resistant to macrolides but susceptible to lincosamides and D-test positive ($> 4/0.5$ ug/ml) will be considered resistant to both macrolides and lincosamides. Susceptibility will be based on the most current CLSI guidelines for each antibiotic or if unavailable, on FDA labeled susceptibility criteria. Antibiotics that define resistance for the class are listed as follows:

- Penicillins – penicillin
- Fluoroquinolones – moxifloxacin
- Cephalosporins – ceftriaxone
- Lincosamides – clindamycin
- Macrolides – azithromycin or erythromycin
- Tetracyclines – tetracycline or doxycycline
- Folate Pathway Inhibitors – Trimethoprim/sulfamethoxazole
- Glycopeptides – vancomycin
- Oxazolidinone – linezolid

If there are multiple specimens (of the same testing modality) from the same time-point where the same pathogen is isolated, only the pathogen with the highest MIC to the test article received will be used. If the pathogens have the same MIC to the test article received, the pathogen with the lowest accession number will be used. The Gram's stain associated with the selected pathogen will be utilized for analysis.

If the same pathogen is identified from the blood and respiratory sample, for tables providing MIC or disk diffusion data, the pathogen with the highest MIC to the test article received will be used.

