11 STUDY DESIGN

11.1 Description

This is a randomized (1:1), double-blind, active comparator-controlled, Phase 3 study comparing omadacycline and moxifloxacin for the treatment of adults with CABP. The number of subjects in Pneumonia Outcomes Research Team (PORT) Risk Class II will be limited to no more than 15% of randomized subjects. Subject randomization will be stratified by PORT Risk Class (II or III/IV), receipt of an allowed antibacterial therapy (see [Appendix 1](#)) in the 72 hours prior to study treatment, and geographic region as defined in the Interactive Voice Response System/Interactive Web Response System (IxRS) specifications and statistical analysis plan (SAP) (see [Section 25.1](#)). All subjects are expected to present with CABP severe enough to require a minimum of at least 3 days of iv treatment.

The study will consist of 3 phases: Screening, Double-Blind Treatment and Follow-up. Following the signing of an ICF, all Screening evaluations, with the exception of the blood culture sample collection and radiographic confirmation of pneumonia, should be completed within the 24 hours prior to randomization. The blood culture sample collection and radiographic confirmation of pneumonia should be completed within the 24 hours prior to the first dose of test article. Subjects who meet inclusion criteria, and do not meet exclusion criteria will be randomly assigned to a treatment group, and should receive their first dose of test article within 4 hours after randomization.

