8.2 Baseline Definition

In general, baseline is defined as the value closest to but prior to the initiation of test article administration. If no test article is received, baseline is defined as the value closest to but prior to randomization.

For pathogen determination, baseline is defined as either Day –1 or 1 (the 24-hour period prior to the administration of the first dose of test article) or if the subject is unable to produce a sputum sample at baseline or the sputum sample does not have an adequate Gram stain, a specimen obtained within 24 hours after the first dose of test article may be used as baseline. If no test article is received, for pathogen determination, Study Day is defined based on date of randomization.

For analyses of vital signs and ECGs, if no value is available prior to the initiation of test article administration, a value within 2 hours after initiation of test article administration can be used as baseline.

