8.6 Visit Windows/Unscheduled Visits

For the primary efficacy outcome, if more than one complete assessment of the symptoms of CABP is done in the Early Clinical Assessment window of 72 to 120 hours after administration of the first dose of test article, the latest will be used. For secondary and additional efficacy outcomes, the data collected at the EOT and PTE Visits, regardless of when these occur will be utilized in the ITT and microITT analyses. The CE and ME populations exclude subjects with a visit occurring outside the window allowed per protocol.

For each safety outcome, analyses will utilize assessments occurring during the scheduled visit windows (provided in [Table 7](#)). Thus, if a subject has a visit outside the scheduled visit window, for example, a PTE Visit occurred 20 days after the subject's last day of therapy, the assessment will not be summarized with the PTE Visit but will be considered an unscheduled assessment. If a subject does not have an assessment at a scheduled visit and an unscheduled assessment was taken within the window for the time point (for example, 5 to 10 days after the subject's last day of therapy for PTE), these assessments will be summarized in the by time point analyses. If more than one measurement is taken during the visit window, the value taken on the scheduled visit will be utilized or if no scheduled visit was done, the first (earliest) measurement in the visit window will be used. If more than one measurement is taken on the same day, the assessment closest to the start of the dose will be used for on treatment values and the last measurement on the day will be used for post-treatment values. For worst overall post-baseline analyses, all assessments including those obtained from unscheduled visits will be included.

Table 7. Scheduled Study Visits

Study Visit	Study Day	Notes
Baseline	Day -1 or Day 1	Except where indicated, last measurement prior to the first dose of test article. Screening assessments are to be taken within 24 hours prior to the first dose of test article. If no test article is taken, the date and time of randomization is used in place of the first dose of test article.
On Treatment	Day 1-Day 10	Day 6 visit is optional for subjects that have been switched to po test article and have been discharged from a hospital setting. A Day 10 visit will be conducted for subjects with treatment extending beyond 9 days, unless this visit coincides with the EOT Visit.

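### The SAP's 24-hour pathogen baseline was not updated to the protocol v2.0 screening window, so an on-protocol specimen 24 to 28 hours old at first dose can fall outside it

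*Combined protocol and SAP*

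**What the plan says.** **Protocol v2.0.** Section 11.1 and Study Flowchart footnote b say that screening evaluations other than blood culture and chest imaging "should be completed within the 24 hours prior to randomization". Blood culture and imaging stay tied to the 24 hours before the first dose. Subjects "should receive their first dose of test article within 4 hours after randomization". Section 17.2.2.1 asks for a further sputum after dosing only if the first was inadequate or could not be obtained. Section 17.2.2.2 collects urine for antigen testing at Screening only.

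**SAP, window.** Section 6.1.3 opens its baseline rule with "In general, baseline is defined as the 24-hour period prior to the administration of the first dose of test article". Section 8.2 labels the pathogen baseline Day -1 or 1 and explains that label as "the 24-hour period prior to the administration of the first dose of test article". Table 7 in Section 8.6 adds "Screening assessments are to be taken within 24 hours prior to the first dose of test article". Section 5.1 and Appendix 1 footnote b give the same 24-hours-before-dose rule for all screening assessments, which was the protocol v1.0 rule.

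**SAP, fallbacks.** Section 6.1.3 also accepts some later samples:
- Sputum, if none could be produced or the Gram stain was inadequate: "a specimen obtained within 24 hours after the first dose of test article may be considered a baseline sample".
- Urinary antigen, if there was no earlier sample or it was negative: "UAT samples up through 24 hours after the first dose of test article may be considered the baseline sample".
- Blood, if there was no earlier sample or it showed no pathogen: "Blood samples up through 24 hours after the first dose of test article may be considered the baseline sample".

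**SAP, declared changes.** Section 7 lists only the addition of the expanded microITT population.

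**The concern.** The protocol amendment moved the reference point for most screening specimens from first dose to randomisation, and added an interval of up to 4 hours between the two. The SAP, finalised later, kept the old reference point in the rule that decides which specimens can supply a baseline pathogen. A site can follow the protocol exactly and still produce a specimen that the analysis discards.

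SAP Section 6.2.2 determines microITT membership programmatically after isolate review, so the wording of the window matters. ME is built from microITT and CE (Section 6.1.5), and the expanded microITT population changes only the Gram stain threshold, so both inherit the rule. These populations carry the by-pathogen response summaries, which serve a stated secondary objective (SAP Section 4.2).

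This looks like carried-over text rather than a choice. SAP Appendix 1 still schedules urine antigen testing at PTE, which protocol v2.0 removed. SAP Section 6.1.4.1 also tolerates imaging taken 24 to 48 hours before dosing for the CE populations, while microbiology specimens get no such allowance.

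**Working it through.** **1. Specimen age at first dose.** Let s be the time from specimen to randomisation and d the time from randomisation to first dose. Protocol v2.0 gives s ≤ 24 h and d ≤ 4 h, so the greatest on-protocol age is s + d = 24 + 4 = 28 h. The SAP requires s + d ≤ 24 h. The gap is 28 − 24 = 4 h. A specimen is on protocol but outside the SAP window when s > 24 − d: with d = 1 h, if taken more than 23 h before randomisation; with d = 4 h, more than 20 h.

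**2. By specimen type.**

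| Specimen | Protocol v2.0 earliest limit | SAP earliest limit | Gap | Post-dose sample accepted by SAP if |
|---|---|---|---|---|
| Respiratory | 24 h before randomisation | 24 h before dose | up to 4 h | no sputum produced, or inadequate |
| Urinary antigen | 24 h before randomisation | 24 h before dose | up to 4 h | none earlier, or negative |
| Acute serology | 24 h before randomisation | 24 h before dose | up to 4 h | not stated |
| Blood culture | 24 h before dose | 24 h before dose | none | none earlier, or no pathogen |

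**3. Do the fallbacks close the gap?** Take an adequate sputum growing a pathogen, collected 26 h before dosing. The protocol asks for no repeat, because the sample was obtained and adequate. Read literally, the SAP fallback is not triggered either, and there would usually be no later sample to use. A positive urinary antigen at 26 h is in the same position. The specimens that carry a pathogen are the ones least likely to be repeated.

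**4. The day label.** Suppose the first dose is at clock hour t on Day 1. Day -1 then begins 24 + t hours before dosing. A 28-hour-old specimen falls on Day -1 when 24 + t ≥ 28, that is t ≥ 4. On a calendar-day reading of Section 8.2, every specimen aged 24 to 28 h is therefore admitted if the first dose is at or after 04:00, and only some if it is earlier. On the hour-based reading, none is admitted. For a late-evening dose the label reaches back almost 48 h. Both readings come from the same sentence.

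**5. The planned microITT figures.** 750 × 0.27 = 202.5, against the stated 202. For power, SAP Table 1 gives 80% in both arms and a 15% margin. It gives no alpha for this column, so one-sided 0.025 is assumed. With 101 per arm, the Farrington-Manning rates under the null are 0.706 and 0.856:
- null standard error: √[(0.706×0.294 + 0.856×0.144)/101] = 0.0572
- standard error under equal rates: √(2×0.8×0.2/101) = 0.0563
- power: Φ[(0.15 − 1.96×0.0572)/0.0563] = Φ(0.672) = 74.9%, against the stated 74%.

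**6. Effect of a loss.** The documents do not give the share of microITT subjects whose only qualifying result is 24 to 28 h old. For assumed shares:

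| Assumed loss | N | Power |
|---|---|---|
| 0% | 202 | 74.9% |
| 1% | 200 | 74.5% |
| 2% | 198 | 74.0% |
| 5% | 192 | 72.7% |
| 10% | 182 | 70.4% |

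**The case against.** Four points can be made for leaving the SAP alone.

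**The SAP does not confine itself to the 24 hours before dosing.** This is correct. A reader of the opening sentence alone might infer that nothing else counts, but the next sentences admit sputum, urine and blood samples after dosing. What remains is that their conditions do not cover an early specimen that was already adequate or positive.

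**Losing a specimen is not losing a subject.** This is also correct. One pathogen from any source is enough for microITT. Blood culture has no gap, and the three atypical pathogens can qualify on a convalescent IgM at PTE. A reader might infer that every affected subject leaves microITT and ME; the definitions do not support that.

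**The wording is loose enough to admit these specimens.** Section 6.1.3 is qualified as a general rule, the Section 8.2 label often admits them, and a blinded Evaluability Review Team looks at isolates. This makes exclusion uncertain, but it does not settle the rule. Section 6.2.2 describes that review in terms of Gram stain and organism identification from baseline samples, and does not name specimen timing.

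**The size is unknown.** A reader might assume specimen times uniform over the 24 h before randomisation and dosing delays uniform over 0 to 4 h. The mean delay is then 2 h, so 2/24 = 8.3% of specimens are too old, and 8.3% of 202 is about 17 subjects. The documents give no such distribution. Blood cultures must fall within 24 h of dosing and protocol Section 14.2 asks for Screening within one day, so specimens taken alongside the cultures are inside the window. The sum also applies a per-specimen chance to all 202 subjects, including those who qualify by other routes. It should not be relied on.

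The protocol does leave population details to the SAP, so a narrower window would be permissible if declared. Section 7 does not declare one.

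**Conclusion.** The mismatch is confirmed: up to 4 hours for respiratory, urinary-antigen and acute-serology specimens, and none for blood cultures. The 28-hour figure is the on-protocol maximum; the 4-hour dosing interval is phrased as an expectation, so it is not a hard cap. The conflict within SAP Section 8.2 is a separate defect, because it leaves the population dependent on which reading is programmed.

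The consequence is minor. The number of subjects affected cannot be derived from the documents and is probably small. Even an assumed 5% loss lowers the planned microITT power by about 2 points (74.9% to 72.7%, at the assumed one-sided alpha of 0.025), and SAP Section 10.3 states no non-inferiority decision rule for that population. The timing in question precedes the first dose of blinded treatment, so no bias between arms is evident. Early Clinical Response in the ITT population does not use the pathogen window and is unaffected. What is at stake is completeness and reproducibility of the microITT, expanded microITT and ME populations and their by-pathogen tables.

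**What to change.** Before database lock:

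- Define the pathogen baseline for respiratory, urinary-antigen and acute-serology specimens as running from 24 hours before randomisation to the first dose.
- Keep the limit of 24 hours before first dose for blood cultures, which already agrees with protocol v2.0.
- Keep the existing post-dose fallbacks.
- In Section 8.2, remove the day label or make it agree with the hour-based window.
- Carry the same rule through SAP Sections 5.1, 6.1.3 and 8.2, Table 7 and Appendix 1 footnote b. Changing only the population section would leave the SAP contradicting itself.

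If the sponsor prefers the narrower window, SAP Section 7 should declare it as a departure from the protocol's screening window.

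The cost is SAP wording and one derivation, with no new data. The downside is that a few specimens up to 4 hours older will count as baseline.
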